5.4.9 Disease Assessment

Imaging assessments, including FDG-PET and CT assessments for Cohorts A and B (PTCL) and CT scan or MRI for Cohort C (TMF), will be performed at Screening and every 8 weeks for the first 3 assessments, then every 12 weeks thereafter, as well as at the time of suspected clinical progression, as described in Schedule of Assessments [REDACTED]. This scheduling is regardless of any treatment/cycle delays that may occur. All imaging assessments will be

conducted according to local institutional practice and the same modality should be used for initial staging at Screening and all restaging assessments.

[REDACTED]

[REDACTED]

[REDACTED]

[REDACTED]

Further details of the conduct and processing of imaging assessments will be described in the Imaging Manual for the study.

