3.3 Study treatments and assessments

AFM13 will be administered intravenously [REDACTED]

[REDACTED] Subjects will be treated weekly until disease progression, unacceptable toxicity, Investigator discretion, or withdrawal of consent. After 16 weeks (from Cycle 2 Day 50 onwards), subjects who are experiencing persistent infusion-related reactions (IRRs) and have achieved an objective response (at least PR) may be dosed on an every other week schedule (Q2W), at the discretion of the Investigator, until disease progression, unacceptable toxicity, Investigator discretion or withdrawal of consent.

A detailed description of procedures and assessments to be conducted during this study is presented in Appendix A of the protocol. A cycle in the study is defined as an 8-weeks period.

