8.6.1.4 Derivation of post-baseline disease assessments visits

In the CRF, the post-baseline disease assessments are not linked to study visits. Consequently, this will be performed by programming as per APPENDIX A.

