As the study design is based on a Simon's two stage design (See Section 5), an exact binomial test will be performed to analysed the ORR of the Cohorts A and C at the final analysis only. The one-sided p-value will be displayed. The tested hypotheses are as follows for each cohort:

Cohort A: $H_0: p \leq 0.25$

$H_1: p > 0.25$

Cohort C: $H_0: p \leq 0.05$

$H_1: p > 0.05$

For all response assessments, swimmer plots will be presented. All response assessments will be also listed.

The above analyses (overall response, BOR and ORR) will be performed for each cohort and for:

Response evaluator	Population of analysis	Analysis order
IRC	FAS	Primary analysis
IRC	FAS with at least one post-baseline efficacy assessment	Sensitivity analysis, if deemed necessary (based on the number of subjects included in that population after the Classification Meeting)
IRC	COVID analysis set	Sensitivity analysis, if deemed necessary (based on the number of subjects included in that population after the Classification Meeting)
IRC	PP set	Sensitivity analysis, if deemed necessary (based on the number of subjects included in that population after the Classification Meeting)
Investigator	FAS	Secondary analysis
██████████	████████████████████	██ ██ ██

These analyses will be also repeated for the subgroups defined in Section 8.8.5 for the FAS.

Duration of response (DOR)

The DOR is defined as time from first assessment of PR or CR to the first assessment of progressive disease or death due to any cause separately for IRC and Investigator using respectively only IRC or Investigator assessments. DOR will be censored for IRC assessments using Table 1 and Investigator assessments using Table 3 when analyses are performed on FAS or PP set. The Table 2 and Table 4 will be used when the analyses are performed on the COVID analysis set:

Final Analysis Statistical Analysis Plan (SAP)

Table 1: Independent Review Committee Assessments (IRC) Censoring Rules

Event	Event or censored date	Event or censored
Progression (as determined by IRC)	Date of progression (as determined by IRC)	Event
Death due to any cause	Date of death	Event
PD (as determined by IRC) or death after 1 missed assessment (ie, ≥ 59 days between 2 assessments until Cycle 4 and ≥ 87 days from Cycle 5)	Date of PD (as determined by IRC) or death	Event

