PD (as determined by IRC) or death after 2 or more missed assessments (ie, ≥ 118 days between 2 assessments until Cycle 4 and ≥ 174 days from Cycle 5)	Date of last disease assessment before missed assessments	Censored
No baseline tumour assessment	Date of first study drug	Censored
No post-baseline response assessment	Date of first study drug	Censored
Start of new anti-cancer therapy before progression (as determined by IRC) or death	Date of last disease assessment prior to new anti-cancer therapy *	Censored
Transplant before progression (progression as determined by IRC) or death or start of new anti-cancer therapy	Date of last disease assessment prior to date of transplant	Censored
No progression determined by IRC or death	Date of last disease assessment	Censored

Note: Only disease assessments provided to IRC are included in the analysis.

* The new anti-cancer therapy information is only collected on the “Survival follow-up” page but no date is collected. Consequently, it is assumed that the new therapy starts between the follow-up where the question “Did the patient start any new anti-cancer therapies?” is “Yes” and the previous follow-up. The subject will be censored at the last disease assessment prior or on this previous visit.

Final Analysis Statistical Analysis Plan (SAP)

[REDACTED]	[REDACTED]	[REDACTED]
[REDACTED]	[REDACTED]	[REDACTED]
[REDACTED]	[REDACTED]	[REDACTED]
[REDACTED]	[REDACTED]	[REDACTED]
[REDACTED]	[REDACTED]	[REDACTED]
[REDACTED]	[REDACTED]	[REDACTED]
[REDACTED]	[REDACTED]	[REDACTED]
[REDACTED]	[REDACTED]	[REDACTED]
[REDACTED]	[REDACTED]	[REDACTED]
[REDACTED]	[REDACTED]	[REDACTED]
[REDACTED]	[REDACTED]	[REDACTED]
[REDACTED]	[REDACTED]	[REDACTED]
[REDACTED]	[REDACTED]	[REDACTED]
[REDACTED]	[REDACTED]	[REDACTED]
[REDACTED]	[REDACTED]	[REDACTED]
[REDACTED]	[REDACTED]	[REDACTED]
[REDACTED]	[REDACTED]	[REDACTED]
[REDACTED]	[REDACTED]	[REDACTED]

Final Analysis Statistical Analysis Plan (SAP)

* The new anti-cancer therapy information is only collected on the “Survival follow-up” page but no date is collected. Consequently, it is assumed that the new therapy starts between the follow-up where the question “Did the patient start any new anti-cancer therapies?” is “Yes” and the previous follow-up. The subject will be censored at the last disease assessment prior or on this previous visit.

Table 3: Investigator Assessments Censoring Rules

Event	Event or censored date	Event or censored

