Progression (as determined by Investigator)	Date of progression (as determined by Investigator)	Event
Death due to any cause	Date of death	Event
PD (as determined by Investigator) or death after 1 missed assessment (ie, \geq 59 days between 2 assessments until Cycle 4, \geq 87 days from Cycle 5 and \geq 122 days from Survival Follow-up)	Date of PD (as determined by Investigator) or death	Event
PD (as determined by Investigator) or death after 2 or more missed assessments (ie, \geq 118 days between 2 assessments until Cycle 4, \geq 174 days from Cycle 5 and \geq 244 days from Survival Follow-up)	Date of last disease assessment or date of last survival contact (for Survival Follow-up) before missed assessments	Censored
No baseline tumour assessment	Date of first study drug	Censored
No post-baseline response assessment	Date of first study drug	Censored
Start of new anti-cancer therapy before progression (as determined by Investigator) or death	Date of last disease assessment or date of last survival contact (for Survival Follow-up) prior to new anti-cancer therapy *	Censored

Final Analysis Statistical Analysis Plan (SAP)

Event	Event or censored date	Event or censored
Transplant before progression (progression as determined by Investigator) or death or start of new anti-cancer therapy	Date of last disease assessment or date of last survival contact (for Survival Follow-up) prior to date of transplant	Censored
No progression determined by Investigator or death	Date of last disease assessment or date of last survival contact (for Survival Follow-up)	Censored

Note: Only disease assessments recorded in the CRF are included in the analysis.

* The new anti-cancer therapy information is only collected on the “Survival follow-up” page but no date is collected. Consequently, it is assumed that the new therapy starts between the follow-up where the question “Did the patient start any new anti-cancer therapies?” is “Yes” and the previous follow-up. The subject will be censored at the last disease assessment prior or on this previous visit.

Final Analysis Statistical Analysis Plan (SAP)

[REDACTED]

[REDACTED]	[REDACTED]	[REDACTED]
[REDACTED]	[REDACTED]	[REDACTED]
[REDACTED]	[REDACTED]	[REDACTED]
[REDACTED]	[REDACTED]	[REDACTED]
[REDACTED]	[REDACTED]	[REDACTED]
[REDACTED]	[REDACTED]	[REDACTED]
[REDACTED]	[REDACTED]	[REDACTED]
[REDACTED]	[REDACTED]	[REDACTED]
[REDACTED]	[REDACTED]	[REDACTED]
[REDACTED]	[REDACTED]	[REDACTED]

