11 APPENDIX A

For each disease assessment visit, the visit name will be derived as follows:

Step 1: Determine the minimum and maximum dates per visit as follows:

For Lugano (within the same disease assessment visit):

DateINF = MIN (

TU.TUDTC (Imaging (modified Lugano)),
TR.TRDTC (Imaging (modified Lugano)),
TU.TUDTC (New Lesions (modified Lugano)),
TR.TRDTC (New Lesions (modified Lugano)),
TU.TUDTC (Tissue Sites Involved),
TR.TRDTC (Tissue Sites Involved),
TU.TUDTC (FDG-PET),
TR.TRDTC (FDG-PET),
PR.PRDTC (FDG-PET))

DateSUP = MAX (

TU.TUDTC (Imaging (modified Lugano)),
TR.TRDTC (Imaging (modified Lugano)),
TU.TUDTC (New Lesions (modified Lugano)),
TR.TRDTC (New Lesions (modified Lugano)),
TU.TUDTC (Tissue Sites Involved),
TR.TRDTC (Tissue Sites Involved),
TU.TUDTC (FDG-PET),
TR.TRDTC (FDG-PET),
PR.PRDTC (FDG-PET))

Final Analysis Statistical Analysis Plan (SAP)

For Olsen (within the same disease assessment visit):

DateINF = MIN (
TU.TUDTC [Imaging (Olsen)],
TR.TRDTC [Imaging (Olsen)],
TU.TUDTC (New Lesions (Olsen)),
TR.TRDTC (New Lesions (Olsen)),
FA.FADTC (TNMB Staging),
QS.QSDTC (mSWAT),
QS.QSDTC (CAILS),
LB.LBDTC (Flow cytometry for Olsen criteria),
PR.PRSTDTC (Lesion Photography),
PR.PRSTDTC (Biospy (Olsen criteria)),
MI.MIDTC (Biospy (Olsen criteria))

DateSUP = MAX (
TU.TUDTC [Imaging (Olsen)],
TR.TRDTC [Imaging (Olsen)],
TU.TUDTC (New Lesions (Olsen)),
TR.TRDTC (New Lesions (Olsen)),
FA.FADTC (TNMB Staging),
QS.QSDTC (mSWAT),
QS.QSDTC (CAILS),
LB.LBDTC (Flow cytometry for Olsen criteria),
PR.PRSTDTC (Lesion Photography),
PR.PRSTDTC (Biospy (Olsen criteria)),
MI.MIDTC (Biospy (Olsen criteria))

Final Analysis Statistical Analysis Plan (SAP)

Step 2: Assign the visit name as follows:

If $(SV.SVSTDTC - 7 \leq DateINF \leq SV.SVSTDTC + 7)$

or $(SV.SVSTDTC - 7 \leq DateSUP \leq SV.SVSTDTC + 7)$

or $(DateINF < SV.SVSTDTC - 7 \text{ AND } DateSUP > SV.SVSTDTC + 7)$ then AVISIT = SV.VISIT;

Else AVISIT = "Unscheduled".

Notes:

- Visits planned per protocol to have disease assessments are considered from SV.
- If at least one assessment of the disease assessment visit is within the time-window then all the assessments are assigned to the visit.

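### The DOR limits for two or more missed assessments (118 and 174 days) do not fit gaps that cross the change from 8- to 12-week imaging, whichever date selects the limit

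*SAP*

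**What the plan says.** Imaging is "every 8 weeks for the first 3 assessments, then every 12 weeks thereafter", "as well as at the time of suspected clinical progression" (Protocol 5.4.9). The same section keeps imaging on this schedule whatever happens to treatment cycles. SAP 3.3 adds: "A cycle in the study is defined as an 8-weeks period".

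SAP 8.6.2, Table 1 (IRC assessments), has two adjacent rows:

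- "PD (as determined by IRC) or death after 1 missed assessment" is an event. The gap is at least 59 days until Cycle 4, or at least 87 days from Cycle 5.
- "PD (as determined by IRC) or death after 2 or more missed assessments" is censored at the last assessment before the missed ones. The gap is at least 118 days until Cycle 4, or at least 174 days from Cycle 5.

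Table 3 (Investigator assessments) uses the same limits for "PD (as determined by Investigator) or death after 2 or more missed assessments", with further limits for Survival Follow-up that are not at issue here. Tables 2 and 4 are redacted.

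**The concern.** The row labels draw a clear line: progressive disease (PD) or death after one missed scan is an event, and after two or more it is censored. The day limits are meant to implement that line, but there are only two of them, split by cycle number, while the imaging interval changes between week 24 and week 36. A gap that spans the change contains one 8-week and one 12-week interval, or starts under one regime and ends under the other. Neither limit is built for such a gap, and nothing visible says whether the cycle is read at its start or its end.

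DOR is a secondary endpoint. It is reported by cohort, separately for CT and PET-CT, for CR and PR separately, and by subgroup, and it is also an interim output. Two programmers could follow the tables faithfully and produce different DOR results.

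**Working it through.** **Inputs.** Days count from first dose. Planned scans (Protocol 5.4.9) are at weeks 8, 16, 24, 36, 48 and 60, that is days 56, 112, 168, 252, 336 and 420. Cycles are 56 days (SAP 3.3), so without delays Cycle 5 starts at 4 × 56 = day 224.

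**The plan's figures.** The one-miss limits are 56 + 3 = 59 and 84 + 3 = 87. The two-miss limits are 2 × (56 + 3) = 118 and 2 × (84 + 3) = 174. They follow a recognisable rule and are not slips.

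**PD on scheduled scans.**

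| Last scan to PD scan | Missed | Gap (days) | Earlier scan selects limit | Later scan selects limit |
|---|---|---|---|---|
| Week 8 to 24 | 1 | 112 | 118: event | 118: event |
| Week 16 to 36 | 1 | 140 | 118: **censored** | 174: event |
| Week 24 to 48 | 1 | 168 | 118: **censored** | 174: event |
| Week 36 to 60 | 1 | 168 | 174: event | 174: event |
| Week 8 to 36 | 2 | 196 | 118: censored | 174: censored |
| Week 16 to 48 | 2 | 224 | 118: censored | 174: censored |
| Week 24 to 60 | 2 | 252 | 118: censored | 174: censored |

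With the earlier scan as selector, two perfectly timed one-miss PDs are censored against their label. With the later scan as selector, all nominal cases are right.

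**PD on an unscheduled scan, or death if the gap is counted to death; later date selects.**

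- Last scan at week 8 (day 56), weeks 16 and 24 missed. Day 224 is a gap of 224 − 56 = 168. Gaps of 118-167 days fall under the 118 limit and are censored. Gaps of 168-173 fall under the 174 limit and are events. Gaps of 174 or more are censored. Two scans are missed throughout.
- Last scan at week 16 (day 112), weeks 24 and 36 missed. With an assumed ±3-day window, week 36 closes at day 255, so both are missed from a gap of 144 days. The 174 limit keeps gaps of 144-173 days as events.

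**The ≥ sign.** With ±3 days at each end, one-miss gaps reach 112 + 6 = 118 and 168 + 6 = 174, and equality censors. For whole-day uniform scatter of ±w days on both scans, the pairs at least 6 days further apart than planned number k(k + 1)/2 with k = 2w − 5 (for w of 3 or more), out of (2w + 1)². This gives:

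- ±2 days: 0/25
- ±3 days: 1/49 = 2.0%
- ±5 days: 15/121 = 12.4%
- ±7 days: 45/225 = 20.0%

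These are shares of one-miss PDs on scheduled scans, later-date reading, excluding week 16 to 36, where the margin is 174 − 140 = 34 days. The protocol's scan window is redacted, so w is an assumption.

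**Simulated effect, later-date reading against a count of missed windows.** Assumptions: first response at week 8 (75%) or week 16 (25%); exponential time to PD with median 60-180 days; 5-20% of scans missed at random; no deaths.

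- All PDs on scheduled scans: the share of all PDs censored against the label is 0% at ±2 days, about 0.1-0.5% at ±3 and about 0.9-4.2% at ±7. The 6-month DOR rate moves by at most about 0.5 points.
- With 30% or 60% of PDs found on unscheduled scans: at most 3.1% are censored and at most 0.2% counted as events against the label. The median moves by at most about 4 days.

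**Earlier-date reading.** Under the same assumptions, with all PDs on scheduled scans, about 3-12% of all PDs are censored against the label even at ±2 days. The resulting change in the DOR estimates is not quantified here.

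**The case against.** **The day limits are the definition.** The rows introduce them with ie, so one can say that the days define the label. But no count of missed scans can turn from censored to event and back as the gap grows, so under the later-date reading the limits cannot be a working version of the label.

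**The anchor may be stated elsewhere.** SAP 7.1 (derived variables) and 7.2 (missing data) are not readable in the public copy. A rule may sit there, so a missing anchor cannot be asserted. Naming either date would still leave one of the two misclassifications above.

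**The limits fit a ±3-day window.** This stands. Protocol 6.8 gives ±3 days for dosing visits after Cycle 1 Day 8. That is not a scan window, but it matches the formula. Within one imaging regime the limits then work, apart from the 1/49 caused by ≥.

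**A stronger reading is tempting.** SAP 8.6.1.4 says that in the CRF "the post-baseline disease assessments are not linked to study visits", and Appendix A then assigns a scan within 7 days of a visit date to that visit. A reader might infer that scans may scatter by ±7 days and that a fifth of one-miss PDs are wrongly censored. The documents do not support this: Appendix A names visits and does not set a permitted scan window. The 12.4% and 20.0% are illustrations only.

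**The effect is small.** This stands for the later-date reading. DOR has no stated hypothesis test, and scheduled PDs after two true misses are always censored correctly.

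**Conclusion.** The two-value limit is wrong as written for gaps that cross the change in imaging interval, and choosing an anchor date does not by itself cure it. The ≥ sign adds a minor fault at the boundary.

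For scale, take Cohort A at its maximum of 103 subjects, an assumed response rate of 25-40% (about 26-41 responders), and progression in every responder:

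- Later-date reading, ±3 days: at most 0.005 × 41 = 0.2 patients misclassified; at ±7 days, at most 0.042 × 41 = 1.7.
- Earlier-date reading, ±2 days: from 0.03 × 26 = 0.8 to 0.12 × 41 = 4.9 patients.

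The bound of about 0.5 points on the 6-month rate belongs to the later-date reading only and should not be carried over to the other. All these figures rest on the simulation assumptions and an assumed scan window. Cycles are counted without delay; because imaging ignores cycle delays, a delayed cycle would move the step at Cycle 5 further from the scan schedule. The primary ORR is untouched. This is a low-priority but worthwhile correction.

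**What to change.** In Tables 1 and 3, replace the 118- and 174-day limits with one rule:

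- The last assessment before the gap selects the limit.
- The limit is the time spanned by the next two planned intervals plus twice the protocol scan window.
- Censor if the gap is greater than (>) the limit; otherwise count an event.

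With a ±3-day window:

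- After week 8: 56 + 56 + 6, so censor at > 118 days.
- After week 16: 56 + 84 + 6, so censor at > 146 days.
- After week 24 or later: 84 + 84 + 6, so censor at > 174 days.

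Replace the 6 days if the protocol window differs. After an unscheduled last scan, count to the second planned assessment that follows it, with the same allowance. State that for a death the gap runs from the last assessment to the date of death. Apply the same rule to Tables 2 and 4 if they carry these limits.

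A one-miss PD with both scans inside their windows can then never be censored. The price is that an off-schedule PD or death up to 6 days below the limit may stay an event although both windows have just closed.

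Do not count windows that closed without a scan. With a ±3-day window, take a last scan at day 56, week 16 missed, and a week-24 PD scan 4 days late at day 172. Both windows have closed, so a count would censor it. Its gap of 116 days is an event under the present limit and under the rule above.

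Cost: SAP wording, minor reprogramming, and a few DOR records that change status. If interim DOR was already produced with the present limits, note the change in the study report.

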8.6.2 Analysis of efficacy endpoints

The primary endpoint is based on the IRC PET-CT-based metabolic responses. Secondary endpoints are based

Final Analysis Statistical Analysis Plan (SAP)

on IRC CT based radiologic responses and on Investigator (CT or FDG-PET (=PET-CT)) responses.

Overall response

Within each visit an overall response will be determined by the IRC and Investigator on CT-based radiographic responses and FDG-PET (=PET-CT) based metabolic responses separately utilizing the modified Lugano Classification revised staging system for malignant lymphoma (Cheson 2014) for Cohorts A and B (PTCL) and the Olsen Criteria (Olsen 2011) for Cohort C (TMF).

Subjects who cannot be evaluated for response will be categorized as not evaluable (NE).

Best overall response (BOR)

The best overall response is the best response recorded from the start of the treatment until disease progression/recurrence or death. All disease responses obtained after progressive disease, start of new anti-cancer therapy or a transplant are excluded from the best overall response. Best is defined as the first response when all a subject's response assessments are sorted by complete response/complete radiologic response/complete metabolic response (CR), partial response/partial remission/partial metabolic response (PR), stable disease/no metabolic response (SD), pseudoprogression, progressive disease/progressive metabolic disease (PD), not evaluable (NE).

The subject's best response assignment will depend on the achievement of the measurement criteria (confirmation is not required). BOR will be summarized using a frequency table by cohort. For Cohorts A and B, BOR is derived for radiographic (using only CT-based responses) and metabolic responses (using only FDG-PET (=PET-CT) based responses) separately.

Overall response rate (ORR)

ORR is calculated as the proportion of subjects with a CR or PR. Subjects without at least one post-baseline response assessment will be treated as non-responders.

ORR and Pearson-Clopper 95% confidence interval (CI) will be displayed separately for CT-based response and FDG-PET (=PET-CT) based response. CR and PR rates and their Pearson-Clopper 95% CI will be also displayed separately.

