Final Analysis Statistical Analysis Plan (SAP)

[REDACTED]	[REDACTED]	[REDACTED]
[REDACTED]	[REDACTED]	[REDACTED]
[REDACTED]	[REDACTED]	[REDACTED]

Note: Only disease assessments collected in the CRF are included in the analysis.

* The new anti-cancer therapy information is only collected on the “Survival follow-up’ page but no date is collected. Consequently, it is assumed that the new therapy starts between the follow-up where the question “Did the patient start any new anti-cancer therapies?” is “Yes” and the previous follow-up. The subject will be censored at the last disease assessment prior or on this previous visit.

DOR will be summarized and listed by cohort and for CT and FDG-PET (=PET-CT) based responses separately. Duration of CR and duration of PR will be also reported separately.

DOR will be analyzed using Kaplan-Meier median, its 95% CI (and 25th and 75th percentile) and the estimates at 3, 6, 9, 12, etc months.

Theses analyses will be also repeated for the subgroups defined in Section 8.8.5 for the FAS.

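### SAP Table 1 censors duration of response at the last disease assessment without requiring that it be evaluable or in the modality analysed, and Table 3 also accepts a survival contact

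*SAP*

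**What the plan says.** SAP 8.6.2 derives DOR "separately for IRC and Investigator using respectively only IRC or Investigator assessments" and states that "DOR will be summarized and listed by cohort and for CT and FDG-PET (=PET-CT) based responses separately". The same section creates an NE category for subjects whose response cannot be evaluated.

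Table 1 (IRC) dates censoring by the last disease assessment in four rows: two or more missed assessments ("Date of last disease assessment before missed assessments"), new anti-cancer therapy, transplant, and no progression or death. One missed assessment is a gap of at least "59 days between 2 assessments until Cycle 4 and" at least 87 days from Cycle 5. Two or more is at least "118 days between 2 assessments until Cycle 4 and" at least 174 days from Cycle 5. The only filter is the table note: "Only disease assessments provided to IRC are included in the analysis".

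Table 3 (Investigator) is worded differently. In the same four rows it also allows the date of the last survival contact. Protocol Section 5 says that these three-monthly checks may be made by telephone or at a routine clinic visit.

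For best overall response the SAP does restrict the modality: "metabolic responses (using only FDG-PET (=PET-CT) based responses) separately". The DOR censoring tables have no such restriction. Protocol 8.6.1.2 leaves detailed censoring rules to the SAP.

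**The concern.** A censoring date should be the last time at which the subject was shown to be still in response. An NE scan shows nothing about response, and a CT without a readable PET shows nothing about metabolic response. If either sets the censoring date, the subject stays at risk, event-free, over an interval in which response was not verified.

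Three features make this the natural result of following the text:

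- The protocol treats disease assessment (the imaging, 5.4.9) and response assessment (the evaluation, 5.4.10) as different things. Table 1 uses both terms. An NE scan is still a disease assessment.
- SAP Appendix A builds one disease assessment visit by pooling CT and FDG-PET dates, so a visit with CT alone qualifies.
- The authors wrote a modality restriction for best overall response but not here.

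DOR is a secondary endpoint of a single-arm study, so no comparator offsets an upward shift. Two programmers could also derive different dates from this text.

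**Working it through.** **1. Schedule and gap limits.** Protocol 5.4.9 puts imaging at Weeks 8, 16 and 24, then every 12 weeks (36, 48, ...). The limits in Table 1 follow if 3 days are added to each interval (the 3 days are inferred, not stated):

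- 8 × 7 + 3 = 59 days; 2 × 59 = 118
- 12 × 7 + 3 = 87 days; 2 × 87 = 174

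Table 3's limits for survival follow-up fit the three months plus one month in SAP 3.1: 91 + 31 = 122; 2 × 122 = 244.

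**2. Single subjects, first response at Week 8, no progression recorded.** DOR = censoring week − 8.

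| Scans | Any scan counts | Last evaluable scan | Difference |
|---|---|---|---|
| Response 8; NE 16; then none | 16 − 8 = 8 weeks | 8 − 8 = 0 weeks | 8 weeks |
| Response 8, 16; NE 24, 36; then none | 36 − 8 = 28 weeks | 16 − 8 = 8 weeks | 20 weeks (8 + 12) |

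Each trailing NE scan adds one interval: 8 weeks (56 days) or 12 weeks (84 days). A scan lacking the modality analysed does the same for that modality. An isolated NE scan often changes nothing: response Week 8, NE Week 16, progression Week 24 is an event at 16 weeks under either reading (112 days, below 118).

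**3. Cohort level.** No NE rate or DOR median is given, so both are assumed: exponential DOR with true median 13 or 26 weeks, each scan independently NE with probability 5%, 10% or 20%, follow-up 8 to 80 weeks after response, and 20,000 responders per setting. The table compares the literal rule with a rule that uses evaluable scans for both the censoring date and the gap count.

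| True median | NE rate | KM at 28 weeks, literal / evaluable | KM at 52 weeks, literal / evaluable |
|---|---|---|---|
| 13 | 5% | 0.232 / 0.227 | 0.064 / 0.061 |
| 13 | 10% | 0.248 / 0.237 | 0.069 / 0.064 |
| 13 | 20% | 0.274 / 0.246 | 0.084 / 0.070 |
| 26 | 5% | 0.479 / 0.475 | 0.255 / 0.251 |
| 26 | 10% | 0.500 / 0.493 | 0.265 / 0.258 |
| 26 | 20% | 0.515 / 0.497 | 0.278 / 0.264 |

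The literal rule is higher in every cell, by 0.3 to 2.8 points. The estimated median is 16 weeks under both rules when the true median is 13. With a true median of 26 and NE of 10% or 20% it is 40 against 28 weeks, but only because the estimate at 28 weeks lies close to 0.50 and medians can fall only on scan dates.

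**4. Separating the two changes.** In a separate run (true median 26, NE 20%), the Kaplan-Meier estimates at 52 weeks were:

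- literal rule: 0.273
- censoring date moved to the last evaluable scan: 0.245
- the same, with NE visits also counted as missed: 0.260
- no NE scans at all: 0.247

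Moving the censoring date alone takes off 0.273 − 0.245 = 2.8 points and lands within 0.2 points of the no-NE value. Counting NE visits as missed then moves the estimate back up by 1.5 points. At 26 weeks, with a true median of 12 and NE 20%, the same addition lowers it (0.445 to 0.427). Its effect is therefore mixed.

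**The case against.** The strongest reply is that the SAP is silent, not wrong. A reader might infer that it instructs programmers to count NE and other-modality scans. It does not say so; the term is undefined in the text that can be read. Sections 7.1 (derived variables) and 7.2 (missing data) and Tables 2 and 4 are not readable in the public copy, and a definition may be there. The modality part is the weaker one: responses are determined separately by modality, DOR is reported that way, and protocol 5.4.9 schedules FDG-PET and CT together for Cohorts A and B. All of this stands, and it limits the point to an unqualified term whose literal reading lengthens DOR.

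A reader might also infer that NE visits must count as missed. Take response at Week 8, NE at Weeks 16 and 24, and progression at Week 36. The longest gap between scans is 84 days, so this is an event at 28 weeks; the gap between evaluable scans is 28 × 7 = 196 days, above both limits. But the limits run between assessments, not evaluable ones. The stricter count would discard an observed progression, and step 4 shows that it does not reliably reduce bias. The documents do not support calling it an error.

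The effect is also small beside sampling error. With 100 Cohort A subjects and an assumed ORR of 25% to 40%, there are 25 to 40 responders. Ignoring censoring, the standard error of an estimate near 0.4 is √(0.4 × 0.6/25) = 0.098 to √(0.4 × 0.6/40) = 0.077. That is a reason for low priority. It does not justify leaving an upward shift that a filter removes.

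**Conclusion.** The point holds as a minor one. As worded, Table 1 lets an NE scan, or one without the modality analysed, set the censoring date, which credits 8 or 12 weeks per trailing scan. Moving the censoring date alone changes Kaplan-Meier estimates by about 0.1 to 3 percentage points, always downward in the settings tried. That range rests on assumed NE rates of 5% to 20%, independent of response status, and assumed true medians of 12 to 26 weeks. No claim is made that the effect concentrates in subjects with poor PET reads, because dependence was not modelled.

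Table 3 should not be read as repeating Table 1. Its survival-contact date is an explicit rule under which Investigator DOR can run on without a scan, by about three months per contact and for as long as contacts continue. The contact does ask about progression, so it is not uninformative, but it is not a response assessment.

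**What to change.** 1. In the censoring rows of Tables 1 and 3, and of Tables 2 and 4 if they are worded alike, replace the last disease assessment with the last evaluable (non-NE) assessment by the same evaluator and in the modality analysed.
2. In Table 3, drop the survival-contact date or confine it to a sensitivity analysis.
3. If Section 7.1 already defines this, a cross-reference in the tables is enough for item 1.
4. Leave the gap limits running between assessments in the main analysis. Counting NE visits as missed can be a sensitivity analysis; it is not a required change.

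The cost is SAP wording and one filter in the derivation program. The downside is slightly shorter censored follow-up.
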